## **Brief Statistical Analysis Plan:**

Briefly, the PCL-5 was considered the primary outcome, while CAPS-5 and MADRS were considered secondary measures. The primary analysis used mixed effects models, with group, time, and group-by-time effects. The secondary analyses examined the rapid and sustained effects of ketamine compared to placebo, at 24 hours post-first and post-last infusion, respectively, by focused contrasts in the mixed models. Sustainability of the effects of ketamine on PTSD symptoms was assessed with similar mixed models for PCL-5 and CAPS-5 during the follow-up period; considering that this analysis included only the responders (non-responders received open label ketamine), we covaried for pretreatment symptom severity. However, there was no difference in pretreatment severity and the results are similar without covarying for severity. The dissociative and psychotomimetic effects were examined using comparable mixed models for CADSS and PANSS, while adding interval (30 minutes vs. 120 minutes) and appropriate interactions to the models.

## Supplemental

Mixed models were constructed to evaluate the effects of posttraumatic stress disorder (PTSD) treatment on the PTSD Checklist for DSM-5 (PCL-5), Clinician-Administered PTSD Scale for DSM-5, Montgomery-Asberg Depression Rating Scale (MADRS), Clinician-Administered Dissociative State Scale (CADSS), and Positive and Negative Syndrome Scale (PANSS) based on all available observations within individual patients. Treatment group (Standard, Low, Placebo), time (pre each infusion, 24 hours post-first and post-last infusions for PCL-5 and MADRS, baseline and post-last infusion for CAPS-5, during each session for CADSS and PANSS), site and all possible interactions were fit as fixed effects. Alcohol use disorder (AUD) diagnosis was included as a covariate. The CADSS and PANSS models also included interval (30 and 120 minutes) and the interaction between interval and treatment. Subject was the clustering factor. The best-fitting variance-covariance structure in each model was selected based on Bayesian information criterion. Residuals were assessed, and CADSS was logtransformed to correct for positive skewness of this outcome. In the final models, nonsignificant interactions not involving treatment were dropped for parsimony. Focused least square mean comparisons of change from baseline to 24 hours post-first infusion and from baseline to 24 hours post-last infusion within treatment group, and for pairwise differences in change from baseline between treatment groups, were evaluated regardless of the significance of the interactions and main effects. Follow-up data on the PCL-5 and CAPS-5 also were analyzed using mixed models covarying for baseline severity. Individuals with open label treatment were excluded from these analyses. Responder status was calculated as at least 25% improvement from pretreatment on the PCL-5. Missing data were treated as failure (i.e., nonresponder). The primary analyses for the binary outcomes were logistic regressions with treatment, site, and AUD as predictors, and missing treated as failure. The treatment by site interactions were nonsignificant and were dropped for parsimony in the final models.

For the PCL-5 self-assessments, 1.6% of assessments specified incorrect index trauma event referenced for symptom scoring, and 23.6% of assessments were completed without specifying the index trauma. A sensitivity analysis determined that mixed methods ANOVA results were essentially unchanged with or without their inclusion.

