
Medical Assessments:

1. Physical exam and health assessment by a licensed physician or Advanced Practice Registered Nurse (APRN).
2. Routine laboratory studies, including: a comprehensive metabolic panel (e.g. electrolytes, hepatic and renal function tests), C-reactive protein (CRP), erythrocyte sedimentation rate (ESR), and urinalysis. Additional tests will be requested as clinically indicated.
3. Breathalyzer tests will be performed at screening and on test days. The results will be determined before proceeding with any infusions.
4. An ECG.
5. A serum/urine pregnancy test will be administered to all reproductive age females enrolled in the study prior to participation and will be repeated pre-infusion on test days.

Length of Assessment Procedures: It is estimated the screening visit to determine subject eligibility will take 6-7 hours. The CAPS-5 interview will take approximately 1 hour, additional clinician-administered assessments may take up to 20 minutes each. Infusion visits will take approximately 6-7 hours, including assessments, any required medical procedures, the infusion, and post-infusion observation. Follow up visits may take 3-7 hours, depending on which

visit and the requirements (see Table 2 for visit requirements). Some visits may take place over more than one day during the study week, depending on the subject's needs.

Study Drug Administration: Subjects will complete 1-2 infusions per week since test days (i.e. ketamine/placebo infusions) will occur at intervals of no less than 2- and no more than 7-days apart. Following an overnight fast, subjects will receive either 0.9% saline, ketamine 0.2 mg/kg, or ketamine 0.5 mg/kg depending on randomization assignment. All study drugs will be intravenously administered and infused over approximately 40 minutes. Randomization will be stratified by study site (i.e. West Haven and San Antonio) and alcohol use disorder comorbidity.

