Primary specific aim: To test the dose-related effects of ketamine on PTSD symptoms in Veterans and active duty military population. We will follow our prior PTSD clinical trial,⁵ using mixed effects regression models, with group, time, group by time effects for the primary outcome variable (PCL-5). We will stratify by infusion center and alcohol use comorbidity. We do not expect to observe significant differences in treatment effects by infusion center but we will test the interaction of treatment group and infusion center and perform follow-up analyses by site as necessary. Similarly, we do not expect significant moderating effects of alcohol use comorbidity but will assess the interaction between treatment and alcohol use comorbidity and perform follow-up tests as necessary. This approach will be applied to most secondary outcome measures as well. Mixed effects regression models use all available data on each subject, are flexible in modeling the correlation structure of the data and give unbiased results under missing at random assumptions. We will select the best-fitting correlation structure for the primary and each secondary outcome based on Schwarz-Bayesian Information Criterion (BIC). Time will be considered as a categorical predictor and post-hoc tests between groups will be conducted for the change from baseline to end-point, which is of primary interest. To assess the trajectory of ketamine effects over time, we will test for linear, quadratic and higher order time trend differences. Post-hoc tests will also be performed to assess whether dose effects are linear. Change in PTSD symptoms is expected to be the largest for the higher dose ketamine group. However, it is possible that the change in the higher dose ketamine group is not significantly different from the change in the lower dose ketamine group. Thus, we will also estimate effect sizes with confidence intervals for the change from baseline to end-point in each group and use this information together with safety data to inform dose selection for potential future studies of ketamine efficacy and evaluation of mechanism of action in PTSD.

In addition to testing the potential moderating effect of comorbid alcohol use described above, we will also perform exploratory analyses to assess moderating effects of depression, medication

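### Alcohol use disorder, a stratification factor, enters the mixed models as a time-constant covariate and so gives the change-from-baseline contrasts essentially no adjustment

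*SAP*

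**What the plan says.** The protocol makes AUD a stratification factor (Study Drug Administration): "Randomization will be stratified by study site (i.e. West Haven and San Antonio) and alcohol use disorder comorbidity". The primary-aim paragraph of its Analysis plan carries this into the analysis: "We will stratify by infusion center and alcohol use comorbidity". The same paragraph commits to assessing whether AUD modifies the treatment effect.

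The Brief Statistical Analysis Plan describes the primary model: "The primary analysis used mixed effects models, with group, time, and group-by-time effects". The SAP Supplemental gives more detail. After listing treatment group and time, it states: "site and all possible interactions were fit as fixed effects". A separate sentence follows: "Alcohol use disorder (AUD) diagnosis was included as a covariate". No AUD interaction is named. Nonsignificant interactions that do not involve treatment were then removed.

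Baseline is one of the outcome times. The focused comparisons are within-group changes from baseline, "and for pairwise differences in change from baseline between treatment groups, were evaluated regardless of the significance of the interactions and main effects". The models are fitted "based on all available observations within individual patients". Responder status (at least 25% PCL-5 improvement) is analysed separately, by logistic regression with treatment, site and AUD as predictors.

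**The concern.** A reader who sees AUD listed as a covariate will take it that the efficacy comparisons are adjusted for it. Whether they are depends on how the term enters the model. With baseline among the outcomes, a single AUD coefficient says that people with AUD score higher or lower by the same amount at every visit. It says nothing about whether they improve more or less. Only an AUD-by-time term does that.

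Two things are at stake. First, if AUD predicts change, the variation it explains stays in the residual of the change contrasts although the randomisation balanced it, so the reported standard errors are larger than they need be. Second, the protocol lists problematic alcohol use as a reason to discontinue. A model that relies on data being missing at random has no AUD-by-time term to absorb dropout linked to AUD.

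**Working it through.** **Inputs from the documents.** 198 randomised, 66 per group; 159 completers, 53 per group (Protocol, Subjects). Implied loss: 1 − 159/198 = 19.7%. Pairwise effect d = 0.6 with 80% power, two-sided 0.05 with Holm-Bonferroni (Protocol, Sample size justification). Ten PCL-5 times: before each of eight infusions, plus 24 hours after the first and the last (SAP Supplemental).

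**Assumed, because the documents are silent.** AUD in about 35% of participants; PCL-5 SD 15; AUD shifts the level by 5 points and the change by 10 points; AUD explains 1% to 10% of the variance in change.

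**Step 1, the plan's own figure.** Power ≈ Φ(d√(n/2) − z). With n = 53, d√(n/2) = 0.6 × √26.5 = 3.089. At two-sided alpha 0.025 (second Holm step) z = 2.241, so power = Φ(0.847) = 80.2%. This reproduces the stated 80%. Alpha 0.05/3 gives 75.6% and alpha 0.05 gives 87.0%.

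**Step 2, cancellation with complete data.** Write the fitted mean for arm g, visit t and AUD status a as m(g,t) + βa. The change is m(g,25) + βa − m(g,0) − βa = m(g,25) − m(g,0), so β drops out. The same holds for the difference between arms and for every component of the group-by-time test, because the weights over visits sum to zero. In simulated complete data (3 × 66 people, 10 visits), the contrast with and without the AUD main effect agreed to about 1e-14, with equal standard errors, under compound symmetry, AR(1) and unstructured covariance. The covariance was held fixed. When it is estimated under a restrictive structure such as AR(1), the AUD term could still nudge its parameters.

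**Step 3, 20% dropout.** Adding the AUD main effect moved the contrast by 0.04 to 0.14 points on average (largest 0.51), against a standard error of about 2.5 to 3.2. The standard error changed by less than 0.01%.

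**Step 4, what AUD-by-time would do to the estimate.** With equal numbers of AUD participants in each arm and complete data, the estimate does not move (difference about 1e-15). With 20% dropout it moves by 0.16 to 0.29 points on average, with no systematic direction. When AUD was left to fall by chance across arms, the average movement was 0.61 to 0.73 points, but stratification exists to limit that imbalance.

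**Step 5, precision.** If AUD explains a share R² of the variance in change, the standard error that ignores it is too large by 1/√(1 − R²) − 1, and the effective standardised difference with AUD-by-time is 0.6/√(1 − R²).

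| R² (assumed) | SE too large by | effective d | power, 53 per group, alpha 0.025 |
|---|---|---|---|
| 0 | 0 | 0.600 | 80.2% |
| 1% | 0.5% | 0.603 | 80.6% |
| 5% | 2.6% | 0.616 | 82.3% |
| 10% | 5.4% | 0.632 | 84.5% |

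**Step 6, dropout linked to AUD.** With no treatment effect and dropout depending on AUD equally in all arms, the contrast was not biased. With 10% dropout without AUD and 45% with AUD in one arm, against 15% in both AUD groups of the comparator, the AUD main-effect model was shifted by about 0.5 to 0.8 points depending on the covariance. The model with AUD-by-time was essentially unshifted.

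**The case against.** The strongest counter-argument is that this hardly matters. Stratification already balances AUD, so leaving out AUD-by-time does not bias the treatment contrast. No document says that AUD predicts change. The upper R² values also need strong effects. With 35% AUD, the gap in change between AUD groups, in residual SDs, is √[R²/(1 − R²)/(0.35 × 0.65)]: 0.21, 0.48 and 0.70 for R² of 1%, 5% and 10%. The last exceeds the d = 0.6 on which the trial is powered. All of this stands, and it limits the point to a modest gain in precision.

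Several stronger readings are tempting, and the documents do not support them:

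- *The AUD term does strictly nothing.* That is exact only with complete data. The models use all available observations and dropout is planned for.
- *The trial's efficacy claims are unadjusted for AUD.* The responder analysis is also a claim about change from baseline, and AUD is one of its predictors.
- *The results are biased by alcohol-related dropout.* That needs dropout to depend on AUD differently by arm, and AUD to predict change. Nothing in the documents shows either, and the protocol plans pattern-mixture sensitivity analyses for disproportionate dropout.
- *The AUD moderation analysis was abandoned.* The SAP calls itself brief and does not mention it. Silence in a summary does not withdraw the protocol's commitment.

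The SAP does not expressly rule out an AUD-by-time term. Had one been fitted, however, the rule on nonsignificant interactions not involving treatment would have removed it unless it was significant.

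**Conclusion.** The point holds for the mixed-model change contrasts on PCL-5, MADRS and CAPS-5 and for the group-by-time test. On the natural reading of the SAP Supplemental, these get no AUD adjustment with complete data and next to none with about 20% dropout, although AUD is a stratification factor and the protocol says the analysis will stratify by it.

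The consequence is small and on the conservative side: standard errors 0.5% to 5.4% too large and 0.4 to 4.3 percentage points of power forgone, if AUD explains 1% to 10% of the variance in change. That range is an assumption. If AUD does not predict change, nothing is lost. Even the constructed case of arm-specific, AUD-related dropout shifted the contrast by less than a third of its standard error (0.8 against 2.5). This is a cheap improvement and does not by itself cast doubt on the direction of the findings.

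**What to change.** Add AUD-by-time to the PCL-5, MADRS and CAPS-5 mixed models, and keep it whether or not it is significant by exempting it from the rule that drops nonsignificant interactions not involving treatment. If it was already in the fitted models, say so in the SAP.

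Report the treatment-by-AUD assessment promised in the protocol as a separate moderation analysis. It should use treatment-by-time-by-AUD, because a treatment-by-AUD term without time would cancel from the change contrasts for the same reason.

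The cost is nine extra parameters in each ten-visit model (PCL-5, MADRS) and one in the two-visit CAPS-5 model, with no new data. The SAP is written in the past tense and reports results, so the models would have to be refitted. Any refit should be labelled as specified after results and shown beside the original fit.
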